10.3.3 Supplementary Analyses of Secondary Endpoints

The secondary endpoints:

- percentage reduction in the time-normalized number of HAE attacks,
- number and percentage of subjects with percentage reductions of $\geq 50\%$, $\geq 70\%$, and $\geq 90\%$,
- time-normalized number of HAE attacks per month requiring on-demand treatment,
- the time-normalized number of moderate or severe HAE attacks,

(see [Section 10.3.2.1](#), [Section 10.3.2.2](#), [Section 10.3.2.3](#)) will be further summarized separately for the first 3 months Treatment Period (Study Day 1 to Day 91), as well as the second 3 months Treatment Period (Study Day 92 to Day 182).

Supplementary Analysis of Secondary Endpoints will be conducted for ITT Analysis Set.

[figure not shown]
HAE attacks

The number and percentage of mild, moderate, and severe HAE attacks will be presented as well as the time-normalized number of mild, moderate, and severe HAE attacks during Run-in Period and Treatment Period.

[figure not shown]
A by-subject listing will show all details per HAE attack sorted by treatment arm, subject-ID and HAE Attack ID including: nominal visit, start and end date:time, anatomical location, severity, on demand treatment taken, potential trigger for this HAE attack.

An additional listing will present absolute number and time-normalized number of all, mild, moderate, and severe HAE attacks per Run-in Period and Treatment Period, duration of Run-in Period and Treatment Period as used for time-normalization for each subject.

[figure not shown]
CCI

[figure not shown]
CCI

CCI

CCI

Time to first HAE attack after Day 1 and after Day 15 during Treatment Period

Time to first HAE attack after Study Day 1 and after Study Day 15 during Treatment Period will be analyzed using the Kaplan-Meier method. Time to first HAE attack after Day 1 will be derived as:

Date of first HAE attack after Study Day 1 – Date of Study Day 1,

and Time to first HAE attack after Day 15 will be derived as:

Date of first HAE attack after Study Day 15 – [Date of Study Day 1 + 14].

Subjects with no HAE attack will be censored at Visit Day 182 or at End of Study Visit (whatever is first). Kaplan-Meier (KM) curves with 95% CI will be plotted by treatment arm showing the percentage of subjects having no attack (subjects under risk) over study days. The corresponding life table will be presented. The median time, the 25% and 75% percentile times until the first HAE attack will be calculated for each treatment arm based on the KM approach. The median time ratio will be calculated for CSL312 against placebo. Summary table will further include minimum and maximum times to the first attacks.

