3.3.2 Dose Rationale

The proposed dose of 200 mg was selected based on the efficacy and safety observed in TP1 of Study CSL312_2001, CSL312 PK, inhibition of FXIIa-mediated kallikrein activity, and exposure-response (E-R) modeling.

The 200 mg dose administered once every 28 days (\pm 3 days) was highly effective across various efficacy endpoints and had a favorable safety profile. In addition, the 200 mg dose resulted in \sim 50% inhibition of FXIIa-mediated kallikrein activity.

To support phase 3 dose selection, an E-R model was used to simulate HAE attack rates over a wide range of CSL312 concentrations that would be expected after different dosing regimens. Based on the E-R model, the estimated daily average concentrations to achieve 50, 75, and 90% relative attack risk reduction in the baseline attack rate were 1.4, 3.3, and 7.8 μ g/mL, respectively. The median predicted minimum daily average CSL312 concentrations at steady-state following 200 mg SC once a month regimen corresponds to the 90% relative attack risk reduction in baseline attack rate in 73% of patients.

Additionally, the E-R model showed a cumulative effect of CSL312 concentration is evidenced in the reduction in the expected number of HAE attacks per month. The 200 mg SC once a month regimen is predicted to reduce the mean attack rate by approximately 91% compared to placebo. Increasing the dose beyond 200 mg is not predicted to result in significant further reductions in HAE attacks.

Finally, the exposures at the 200 mg SC dose administered monthly are not expected to cause aPTT prolongation in the majority of subjects in the phase 3 study.

Based on all the factors taken into consideration in selecting a dose for advancing the CSL312 clinical program, the 200 mg of CSL312 SC administered once monthly is expected to achieve clinically meaningful treatment effect and optimal benefit/risk ratio in subjects with C1-INH HAE type 1 and type 2.

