4.5 Determination of the Sample Size

In total, 60 subjects are planned to be randomized.

Forty subjects with C1-INH HAE type 1 and type 2 completing the 6-month Treatment Period are needed to achieve a power of approximately 90% for a two-sided Wilcoxon Test (alpha of 5%). Subjects will be randomized to the Active Arm or the Placebo Arm with a ratio of 3:2. An attack rate per month of 0.3125 for CSL312-treated subjects and of 1.3 for subjects receiving placebo are assumed. The monthly attack rates of placebo and of CSL312 are assumed to be Poisson distributed.

The sample size calculation is performed with SAS 9.4 using proc power procedure with twosamplewilcoxon test=WMW which performs power analyses for the Wilcoxon-Test for two independent groups, i.e. the CSL312 and the Placebo treatment in Study CSL312_3001. The Wilcoxon Rank Sum test is testing from departure from the null hypothesis and is assessing if there is a location shift between the distributions of the HAE attack rates of the CSL312 and the Placebo treatment. SAS Proc Power procedure uses the O'Brien-Castelloe approach to compute approximate power. Alpha is set to 5% [O'Brien & Castelloe, 2006]. The assumed monthly attack rates of placebo and of CSL312 (i.e. 1.3 and 0.3125 attacks/month, respectively) are used as the two means of the two Poisson distributions. The randomization ratio of 3:2 was implemented by GROUPNS = (24 16) resulting in a total sample size of 40 which is the lowest one reaching 90% power.

It is targeted to randomize approximately 5 adolescents into the treatment period with a randomization ratio of 3:2 (active:placebo).

To allow for sufficient safety data, to increase the likelihood of adolescents entering the study and, to have at least 40 subjects reaching the end of the study, an additional 20 subjects are planned to be randomized.

In case it is not feasible to randomize the targeted number of adolescents, the targeted total sample size will be achieved by randomizing the needed number with adult subjects.

In addition, it is targeted to include 5 Japanese subjects into the total 60 subjects randomized.

Based on Method 1 and Method 2 in the [Basic principles on Global Clinical Trials] the sample size of the Japanese subjects are planned as below. The point estimate of the endpoint in each arm for Japanese population and other regions (for Method 2) are assumed as the same as that for the global population.

Method 1

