10.1 Analysis of Primary Endpoint

The primary endpoint is the time-normalized number of HAE attacks per month during the Treatment Period from Day 1 (first study drug administration) through Day 182 (inclusive).

Subjects will enter HAE symptoms into their eDiary, the start and end date and time, the interference of HAE symptom(s) with daily activities, and location(s) of the HAE symptom(s). Investigator-reported HAE attacks will be based upon review of subject diaries, relevant interval medical history, and physician judgment. The investigator may ask clarifying questions to assist in his/her assessment of whether or not an HAE attack occurred. If an attack occurred, then the investigator will record an attack in the eCRF form, the start/end date and time, the attack location(s), and the severity of the attack based on the most severe symptoms. For every visit, the investigator will report all HAE attacks that have occurred in the interim since the last visit the subject attended.

For all analyses considering HAE attacks, only the HAE attacks confirmed and reported by the investigator using the eCRF ‘HAE Attacks’ form will be used.

HAE attacks with a start date on or after the first day of the Run-in Period but prior to the date and time of the first study drug administration will be counted for the Run-in Period.

HAE attacks with a start date and time after the first study drug administration through Visit Day 182 (inclusive) or End of Study visit (whatever is first) will be counted for the Treatment Period and will be included in the analyses of efficacy.

The primary endpoint will be analyzed using the ITT and PP Analysis Set. The ITT Analysis Set will be used as the primary analysis and the PP Analysis Set will be used as the supplementary analysis (see [Section 10.1.3](#)).

The primary endpoint, time-normalized number of HAE attacks per month, is calculated per subject as:

$$[\text{the number of HAE attacks} / \text{length of subject treatment in days}] * 30.4375$$

where the length of subject treatment is calculated as:

$$[\text{the date of Study Visit Day 182 or the End of Study date [whatever is first]} - \text{the date of Study Visit Day 1 of the Treatment Period} + 1].$$

To transform the length of subject treatment which are calculated in days in years the number of days is divided by 365.25. Thus, time-normalized number of HAE attacks per year is calculated per subject as:

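### Time to first attack: the only planned between-arm figure is a ratio of Kaplan-Meier medians with no CI or test, uncomputable in about half of trials if the predicted 91% effect meets the planning placebo rate; the Day 15 rule can also give negative times

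*SAP*

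**What the plan says.** Protocol 2.3.2 lists time to first attack after Day 1 and after Day 15 as exploratory, and Protocol 10.3.7 leaves its analysis to the SAP. The SAP subsection on time to first HAE attack (after 10.3.3, before 10.5) plans Kaplan-Meier curves with 95% CIs by arm, a life table, the quartiles and median per arm, and minimum and maximum times. The one figure that compares the arms is: "The median time ratio will be calculated for CSL312 against placebo".

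The Day 15 time runs from the date of Day 1 plus 14 days to the "Date of first HAE attack after Study Day 15". The Day 1 time uses the first attack after Study Day 1, as a difference of dates. For censoring: "Subjects with no HAE attack will be censored at Visit Day 182 or at End of Study Visit (whatever is first").

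SAP 10.1 defines Treatment Period attacks by date and time: "HAE attacks with a start date and time after the first study drug administration through Visit Day 182 (inclusive"), which includes attacks later on the dosing day.

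On effect size, Protocol 3.3.2 says the regimen is "predicted to reduce the mean attack rate by approximately 91% compared to placebo". SAP 4.5 plans on a smaller effect: "An attack rate per month of 0.3125 for CSL312-treated subjects and of 1.3 for subjects receiving placebo are assumed".

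**The concern.** A ratio of medians exists only if both curves fall to 50%. The better the drug works, the less likely the CSL312 curve is to get there by Day 182. The planned contrast is therefore most fragile when the effect is largest, and the visible text does not say what is reported instead. Even when the ratio can be computed, it has no interval.

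The time rules raise a second issue. Nothing restricts the Day 15 analysis to subjects still in the study on Day 15, so the censoring date can precede the time origin. The SAP's rule that treats the attack rate as missing for subjects who discontinue within 30 days (8.1, 10.1) is written for the rate and is not carried over to this endpoint. The Day 1 event definition also does not match SAP 10.1.

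**Working it through.** **Inputs.** Rates of 0.3125 and 1.3 per month, Poisson (SAP 4.5); a 91% reduction (Protocol 3.3.2); 36 CSL312 and 24 placebo subjects (SAP 4.5); a month of 30.4375 days (SAP 8.2.2). Follow-up to Day 182 is 181 days from Day 1 and 167 days from Day 15. The documents give no dropout rate and no amount of between-subject heterogeneity, so both are varied below as assumptions.

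**The plan's own figure.** The documents state no figure for this endpoint. The SAP's power for the primary test ("power of approximately 90% for a two-sided Wilcoxon Test (alpha of 5"%), 24 + 16 subjects) recomputes to 90.7% by the O'Brien-Castelloe approximation and 91.6% by simulation, so the planning inputs are read correctly.

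**Is the median reached?** With a constant rate r per month, the attack-free share after T days is exp(−rT/30.4375) and the median time is 30.4375 × ln 2 / r.

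- Placebo at 1.3: median 16.2 days; the attack-free share at 181 days is 0.04%. The placebo median is always reached.
- CSL312 at 0.3125: median 67.5 days.
- CSL312 at 0.09 × 1.3 = 0.117: median 180.3 days, against 181 days available from Day 1 and 167 from Day 15.

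With complete follow-up the CSL312 median is missing when 17 or fewer of 36 have an attack. That is a binomial probability with event probability 1 − exp(−rT/30.4375). A curve that ends exactly at 50% is counted as reached.

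| CSL312 rate per month | Attack-free, Day 1 / Day 15 | Median not reached, Day 1 / Day 15 | Same, gamma shape 2 | Same, gamma shape 1 |
|---|---|---|---|---|
| 0.3125 (planning) | 16% / 18% | 0% / 0% | 0.1% / 0.2% | 2% / 4% |
| 0.117 (91% of 1.3) | 49.9% / 52.6% | 43% / 56% | 67% / 76% | 82% / 88% |
| 0.18 (91% of 2.0) | 34% / 37% | 2% / 4% | 14% / 21% | 35% / 45% |
| 0.27 (91% of 3.0) | 20% / 23% | 0% / 0% | 0.5% / 1% | 6% / 9% |

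The attack-free column has no heterogeneity. In the gamma columns the share is (1 + rT/(30.4375k))^(−k), where k is the shape. The placebo rates 2.0 and 3.0 are assumptions. In simulation at 0.117, losing one third of subjects gives 49% / 59%. When the ratio does exist at 0.117, its 2.5th to 97.5th percentile range is about 5 to 20.

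**What a hazard-based contrast would have.** Expected first attacks at the 91% effect: 24 × 0.9996 + 36 × 0.501 = 42. At the planning effect: 24 × 0.9996 + 36 × 0.844 = 54. Schoenfeld's formula for 90% power at 3:2, (1.96 + 1.28)² / (0.6 × 0.4 × (ln HR)²), gives 8 events at HR 0.09 and 22 at HR 0.24. Simulated log-rank power is about 100% in both cases without heterogeneity. At the planning effect it falls to 96% (shape 2) and 82% to 85% (shape 1, two simulation runs).

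**Time rules.**

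- *Leaving before Day 15.* End of Study on Day 10 is Day 1 + 9, so the censoring time is 9 − 14 = −5 days. The number affected is 0 if nobody leaves early. If one third leave at a constant hazard (an assumption, taken from the 20 extra subjects among 60), it is 60 × [1 − (2/3)^(14/181)] = 1.9.
- *Dosing-day attacks.* With half a day left after dosing (assumed), the expected number in the placebo arm is 24 × 1.3 × 0.5 / 30.4375 = 0.5.
- *Attack only before Day 15.* Expected in the CSL312 arm at 0.117: 36 × [1 − exp(−0.117 × 14/30.4375)] × exp(−0.117 × 167/30.4375) = 1.0. At 0.3125 it is 0.9.

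**The case against.** The strongest reply is that the high failure rates depend on one pairing. Protocol 3.3.2 attaches no placebo rate to its 91%, and 1.3 belongs to a planning scenario with a smaller effect, in which the ratio almost always exists. SAP 10.1 expects about half of subjects to have at least 3 attacks per month at baseline, which would make the placebo rate higher and the problem smaller. The gamma shapes appear nowhere in the documents. All of this stands, so the failure chance is conditional.

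A reader might also infer that the endpoint could yield no comparison at all. The documents do not support that. Per-arm curves, life tables and quartiles remain, and the CSL312 25% time is unreached in at most about 1.5% of trials from Day 1 and 2.5% from Day 15 in the scenarios above. SAP 10.3.2.1 already plans attack-free percentages with CIs and Fisher tests for 6 months and for each 3-month half.

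The hazard ratio has limits too. Heterogeneity pulls it toward 1: at a 91% effect with placebo 1.3, the median fitted value is 0.15 (shape 2) or 0.21 (shape 1), against a rate ratio of 0.09.

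On timing, two stronger readings are tempting. One is that the Day 1 rule produces invalid times. It does not: a dosing-day attack gets time zero or is passed over for a later one, so the defect is inconsistency with SAP 10.1. The other is that a subject whose only attack came before Day 15 has no valid time. Because the event is an attack after Day 15, the natural reading is that this subject is censored.

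**Conclusion.** The point holds in a limited form. In the visible text, a bare ratio of medians is the only between-arm figure. It has a 43% (Day 1) or 56% (Day 15) chance of being uncomputable if a 91% reduction meets a placebo rate of 1.3, assuming 36 subjects, constant rates and complete follow-up; assumed heterogeneity raises this. At the planning rate of 0.3125 the chance is about 0% to 4%, even with the assumed heterogeneity. At a 91% effect with placebo 2.0 or more and no heterogeneity it is also about 0% to 4%. It would be wrong to say without these conditions that the ratio will often be missing.

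Of the timing points, only the negative censoring time for subjects who leave before Day 15 is a true failure of the rule. The Day 1 wording is an inconsistency affecting about half a placebo subject in expectation.

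The consequence is small: the endpoint is exploratory and outside the testing hierarchy of SAP 10.5. Text near this subsection is redacted, but the subsection itself reads as complete.

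**What to change.** Keep the Kaplan-Meier summaries. Add a log-rank test and a Cox hazard ratio with 95% CI, or the restricted-mean difference to Day 182 with 95% CI. Report the median ratio only when both medians are reached.

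For the time rules:

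- Limit the Day 15 analysis to subjects still under observation on Day 15.
- State that subjects with no attack after Day 15 are censored at Day 182 or End of Study, whichever is first.
- In the Day 1 analysis, count attacks after the first dose, as SAP 10.1 does.

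The cost is a few SAP sentences and one more procedure call. The primary analysis, the alpha and the conduct of the trial do not change. The hazard ratio assumes roughly proportional hazards and is attenuated by between-subject heterogeneity; the restricted-mean option avoids the proportionality assumption.

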10.5 Multiple Comparisons and Multiplicity

Four test one for the primary endpoint (H01) and 3 for the 3 secondary endpoints (H02, H03, H04) will be performed in a hierarchical order with an 2-sided alpha of 5% each, see [Section 4.2](#). Four null hypotheses are defined:

- H01: the time-normalized number of HAE attacks in the first 6-month time period of the Active Arm and in the Placebo Arm period are equal.
- H02: the percentage reduction in means of the time-normalized number of HAE attacks for the 6-months of the Active Arm compared to the 6-month Placebo Arm period are equal.
- H03: the number of subjects who do not experience a HAE attack in the first 3 months of the Active Arm and the first 3-months of the Placebo Period are equal.
- H04: the percent of subjects with good or excellent responses to the ~~cci~~ at the end of Treatment Period (Day 182) are equal for subjects treated with CSL312 and placebo.

The general process flow of the hypothesis testing is as follows:

the null hypothesis associated with the primary endpoint H01 will be tested first. If and only if the resulting 2-sided p-value is < 0.05 , testing of H02 will be performed. If and only if H02 can be rejected (2-sided p-value < 0.05), H03 is tested at 2-sided alpha of 5%. If and only if H03 can be rejected (2-sided p-value < 0.05), H04 is tested at 2-sided alpha of 5%.

This hierarchical testing procedure controls for the overall alpha level of 5%. All other tests will be performed with 2-sided alpha of 5% in an exploratory manner.

10.6 Treatment Compliance

Compliance will be summarized for the Safety Analysis Set for all injections administered during the Treatment Period.

The 1.2 mL prefilled syringes contain 200 mg garadacimab (CSL312) at a concentration of 170 mg per 1 mL. A loading does will be administered by the use of two pre-filled syringes and every subsequent dose will be administered by use of one pre-filled syringe. In eCRF only the information is collected if one or two syringes have been administered and if the full volume of the study drug for that injection was administered (Yes, No). The actual administered mL is not documented.

Technical Note: The loading dose will be treated as one injection for all calculations defined in this SAP even though the administration will require the use of two syringes and will have two kit numbers recorded in the CRF.

Thus, treatment compliance will be based on number injection with 'was the full volume of the study drug administered' answered with 'Yes' in relation to the planned number of injections.

Treatment compliance for each subject will be derived for the Treatment Period as:

$$\text{Treatment compliance (\%)} = 100 \times (\text{Number of injections with full volume administered} / \text{Total planned number of injections}),$$

with Total planned number of injection is 6 per CSP (once per month within 6-month Treatment Period).

Treatment Compliance as well as details for device malfunctions or other errors will be summarized using descriptive statistics along with further exposure data (see Section 11.1).

11 Safety Analyses

Safety data will be summarized using the Safety Analysis Set.

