3.2 Dose and Dosing Regimen

The investigational products in this study are 200 mg CSL312 and placebo.

Subjects randomized to the Active Arm will receive CSL312 SC once a month for 6 months. The first dose of CSL312 will be a 400 mg loading dose administered subcutaneously on the same day as 2 separate injections at the study site (ie, Month 1). Subsequent doses of CSL312 will be 200 mg administered SC once monthly for 5 consecutive months (ie, Months 2 through 6).

Subjects randomized to the Placebo Arm will receive volume-matched placebo once monthly for 6 months. The first dose of placebo in the Placebo Arm will be volume-matched placebo administered SC as 2 separate injections (ie, Month 1). Subjects will then receive volume-matched placebo SC once a month for 5 consecutive months (ie, Months 2 through 6).

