5.1.3 Dosing and Administration

The investigator (or delegate) will administer or dispense CSL312 only to subjects included in this study following the procedures set out in this study protocol. Information on the dosing characteristics of CSL312 is provided in Table 3.

Table 3 Investigational Product Dosing Characteristics

	Investigational Product	
Administration parameter	CSL312	Placebo
Dose	200 mg	Not applicable
Route	Subcutaneous	Subcutaneous
Anatomical Location	Abdomen	Abdomen
Total infusion volume	1.2 mL	1.2 mL

The first dose of CSL312 or placebo will be a SC loading dose consisting of 2 separate injections of 200 mg CSL312 for a total of 400 mg CSL312 or volume-matched placebo. After obtaining the administration training, the first 3 SC administrations will be self-administrated by the subjects or caregivers under the supervision of the investigator or delegate during the study site visits (ie. Day 1, 31, and 61). Subsequent doses can be self-administrated with (if deemed necessary by the investigator) or without supervision of the investigator or delegate.

Detailed information on the preparation and administration of CSL312 or placebo is provided in the Site Investigational Product Manual.

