9.2 Protocol Deviations

All identified protocol deviations throughout the study will be listed prior to database lock and will be classified into minor/major by CSL. Major protocol deviations are defined as deviations that could have a significant effect on the subject's safety, rights, or welfare and/or on the integrity of the study data.

The protocol deviations' classification into minor and major will be reassessed under statistical considerations. During the blinded data review meeting (BDRM), the classification and the subject's assignment to any analysis set will be discussed in detail. The decisions made during the BDRM will be documented in the BDRM minutes and agreed upon prior to database lock for final analysis.

Table 9 Potential Protocol Deviations

Potential Protocol Deviations	Potential Exclusion From Analysis Set
Subject did not provide informed consent and/or informed consent date missing	Screening, SAF, ITT, PP, PK, PD
Subject randomized but not treated with study treatment	SAF, PP, PK, PD
Subjects treated with incorrect study treatment	PP, PK, PD
Subject randomized and treated but does not have at least one measurable PK concentration	PK
Subject randomized and treated but does not have at least one PD measurement	PD
Subject randomized and treated but without primary efficacy assessment	PP
Subject randomized and treated but violated inclusion and/or exclusion criteria	PP, (SAF, ITT, PK, PD)
Subject randomized and treated but compliance outside 80-120%	PP, (PK, PD)
Subject randomized and treated but received prohibited concomitant medication	PP, (PK, PD)
Subject with COVID-19 diagnosis	PP (SAF, PK, PD)

Protocol deviations caused by the COVID-19 pandemic will be documented throughout the entire study. They will be assigned as a separate protocol deviation category "other" with free-text "COVID-19" and discussed during the Blinded Data Review Meeting. COVID-19 related protocol deviations will be summarized and listed separately from all other protocol deviations and will also be discussed in the CSR.

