 - TEAEs by outcome (Death, Not Recovered or Not Resolved, Recovered or Resolved, Recovered or Resolved with Sequelae, Recovering or Resolving, Unknown);
 - TEAE identified as Injection Site Reaction (ISR);
 - ISRs related to study drug;
 - ISRs by severity;
- Any Serious TEAEs (SAEs);
 - SAEs related to study drug;
 - SAEs leading to study discontinuation;
 - SAE temporally related;
 - SAEs by severity (Mild, Moderate, Severe);
 - SAEs by outcome (Death, Not Recovered or Not Resolved, Recovered or Resolved, Recovered or Resolved with Sequelae, Recovering or Resolving, Unknown).

The following summary tables will be provided:

- All TEAEs by SOC and PT,
- All TEAEs leading to study discontinuation by SOC and PT,
- All TEAEs by severity and by SOC and PT,
- All TEAEs related to study drug by SOC and PT,
- All AESI by SOC and PT,
- All ISRs by SOC and PT,
- All SAEs by SOC and PT,
- All Non-serious TEAEs by SOC and PT,
- Laboratory Findings reported as AEs,
- All AEs caused by COVID-19 (see [Section 7.1](#)),
- TEAEs occurring 7 days of COVID-19 vaccine administration (see [Section 7.1](#)),
- All TEAEs excluding TEAEs occurring within 7 days of COVID-19 vaccine administration.

Summaries will include the number and percentage of subjects, the number of TEAEs, and the number of TEAEs per injection and per subject year (where applicable) derived as:

$$\text{TEAE rate per SC Injection (AERI)} = \frac{\text{Number of Events for particular SOC/PT}}{\text{Number of SC Injections}};$$

$$\text{and TEAE rate per Subject SC Year (AERS)} = \frac{\text{Number of Events for particular SOC/PT}}{\text{Subject SC years}}.$$

where subject SC years will be the sum of the time in years that subjects were exposed to study drug administered by SC injections derived as:

[date of Study Completion or date of study discontinuation [whatever is first] – the date of Study Visits Day 1 within Treatment Period +1] / 365.25.

All AEs (treatment-emergent and non treatment-emergent) will be listed including MedDRA SOC, PT and verbatim, AE start and end date:time, duration of AEs in days, intensity, serious status, relationship to study drug, outcome, action taken, and AE flags (TEAES, SAE, AESI, clinically significant laboratory finding, temporal relationship).

The following listings will be provided:

- All Non-TEAEs,
- All TEAEs,
- All TEAEs leading to study discontinuation,
- All TEAEs related to laboratory findings,
- All TEAEs caused by COVID-19,

- All SAEs,

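### SAP 10.6 counts the two-injection loading dose as one injection, so the adverse event rate labelled per SC injection is about one sixth too high for a full course

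*SAP*

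**What the plan says.** Protocol 5.1.3 states: "The first dose of CSL312 or placebo will be a SC loading dose consisting of 2 separate injections of 200 mg CSL312". Protocol 3.2 agrees, "The first dose of CSL312 will be a 400 mg loading dose administered subcutaneously on the same day as 2 separate injections", and continues "Subsequent doses of CSL312 will be 200 mg administered SC once monthly for 5 consecutive months". SAP 4.3 repeats this regimen. Placebo subjects also receive two injections at the first dose.

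SAP 10.6 sets a different counting rule: "The loading dose will be treated as one injection for all calculations defined in this SAP". The same note acknowledges that two syringes are used and that two kit numbers are recorded. Compliance is the number of injections given at full volume divided by the planned number, "with Total planned number of injection is 6 per CSP (once per month within 6-month Treatment Period". On data capture, the section says "In eCRF only the information is collected if one or two syringes have been administered", along with a yes/no answer on full volume.

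SAP 11.2 promises "the number of TEAEs per injection and per subject year (where applicable) derived as" and defines the first of these (AERI) as events divided by the number of SC injections. The tables it lists include one for injection site reactions. Protocol 10.3.3 plans adverse events per injection and gives the word no special meaning. SAP section 5, on changes from the protocol, does not mention the counting rule and says there are no further changes.

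On compliance limits, SAP 11.1 uses two categories, below 80% and 80–100%. SAP Table 9 lists as a potential deviation "Subject randomized and treated but compliance outside 80-120" percent.

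**The concern.** A rate labelled per SC injection should be divided by injections, and both documents say that the first dose is two of them. The redefinition sits in a technical note on compliance, not beside the rate in SAP 11.2, so someone reading the report table will take the label literally.

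The rate matters most for injection site reactions, where the injection is the natural unit. Protocol 1.2.3.2 reports these as the most frequent adverse events in phase 2. Protocol 1.2.3.1 reports that in phase 1 they were more common with SC CSL312 than with SC placebo. What is at stake is the accuracy of an absolute descriptive safety figure, not any test or decision rule.

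There is a related gap in compliance. The number of syringes is recorded, but the formula does not use it, and the two stated ranges disagree on the upper limit.

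**Working it through.** **Inputs.** Loading dose: 2 injections (Protocol 3.2 and 5.1.3, SAP 4.3). Later doses: 5, with one injection each (Protocol 3.2; Schedule of Assessments, footnote T). SAP rule: the loading dose counts as 1 (SAP 10.6). Planned arm sizes: 36 CSL312 and 24 placebo (SAP 4.5).

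**Reproducing the SAP's figure.** 1 + 5 = 6, which is the planned total in SAP 10.6. Counting actual injections gives 2 + 5 = 7.

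**Excess for one subject.** With both loading syringes given and k dosing occasions, the SAP counts k injections and the subject receives k + 1. The SAP rate divided by the rate per actual injection is (k + 1)/k.

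| Dosing occasions k | SAP count | Actual injections | Excess |
|---|---|---|---|
| 6 | 6 | 7 | 16.7% |
| 5 | 5 | 6 | 20% |
| 4 | 4 | 5 | 25% |
| 3 | 3 | 4 | 33% |
| 2 | 2 | 3 | 50% |
| 1 | 1 | 2 | 100% |

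**Pooled over an arm, all completing.** CSL312: 36 × 6 = 216 against 36 × 7 = 252. Placebo: 24 × 6 = 144 against 24 × 7 = 168. Both ratios are 7/6, an excess of 16.7%. Put the other way, the per-injection rate is 1 − 6/7 = 14.3% below the SAP figure.

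**Pooled, with early stopping (assumed shares).** With mean occasions m, the excess is (m + 1)/m − 1.
- 10% stop after one dose: m = 0.9 × 6 + 0.1 × 1 = 5.5, excess 18.2%.
- 20% stop after three doses: m = 0.8 × 6 + 0.2 × 3 = 5.4, excess 18.5%.
- 20% stop after one dose: m = 0.8 × 6 + 0.2 × 1 = 5.0, excess 20.0%.

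**Pooled, with some subjects given only one loading syringe (assumed shares, all completing).** The excess is (7 − q)/6 − 1: 15.8% for q = 5% and 15.0% for q = 10%.

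**Effect on the between-arm ratio.** If both arms complete, 7/6 cancels. If 10% of one arm only stop after one dose, the ratio moves by a factor of (6.5/5.5)/(7/6) = 1.013, or about 1.3%.

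**Compliance.** A full course scores 6/6 = 100%. If one loading syringe is not given, the score is 5/6 = 83.3% or 6/6 = 100%, depending on how the full-volume question is answered for that dose; by syringe it would be 6/7 = 85.7%. One unplanned syringe at a later visit leaves 100% if the visit counts as one injection, or gives 7/6 = 116.7% if it counts as another. The SAP does not say which applies.

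**The case against.** The best defence is that the convention is disclosed and coherent. SAP 10.6 says openly that two syringes count as one injection, and the planned total of 6 follows. Read as a rate per dosing occasion, AERI is correct, and for systemic events the occasion is a sensible unit. The rule is the same in both arms, and the error makes the drug look slightly worse rather than better. The safety endpoints are numbers and percentages of subjects, and no hypothesis test uses AERI. All of this stands and limits the severity. It does not repair the label: the documents call the first dose two injections, and the table will say per SC injection.

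Several stronger readings are tempting, and the documents do not support them:

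- **That extra syringes can never appear in compliance, so the upper 120% limit is dead.** The one-injection note names only the loading dose. How an unplanned later syringe is counted is left open.
- **That the per-protocol set has no protection against over-dosing.** The compliance percentage is one of several potential deviations in Table 9. All identified deviations are listed and classified, and assignment to analysis sets is discussed at the blinded review (SAP 9.2). SAP 11.1 lists every injection record and counts use errors.
- **That dropout distorts the rate badly.** The 33% and 100% figures belong to single subjects; the pooled rate moves by a point or two in the 10% and three-dose cases above.
- **That reactions at both Day 1 sites are always counted twice in the numerator.** Neither document says how same-day reactions at two sites are entered.

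**Conclusion.** The point holds as a mislabelled denominator. The exposure count of SC injections and the TEAE rate per SC injection, including the rate for injection site reactions, use 6 where a completer receives 7. The absolute rate is 16.7% too high if all subjects receive both loading syringes and complete. It is somewhat higher with early stopping and slightly lower if some subjects receive only one loading syringe; the stopping and missed-syringe shares used here are assumptions.

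A reader might infer that the safety comparison between arms is biased, or that efficacy is touched. Neither follows. Subject incidence and per-subject-year rates do not use this denominator, the between-arm ratio is essentially unchanged when dosing is similar, and no efficacy analysis involves it.

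The mismatch between the 80–100% and 80–120% ranges, and the silence on missing or extra syringes, are separate gaps to close. Overall severity is minor.

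**What to change.** 1. In SAP 10.6, limit the one-injection convention to the per-occasion compliance count and remove its extension to every calculation in the SAP.
2. In SAP 11.1 and 11.2, use the recorded number of syringes injected (two for a complete loading dose) for the number of SC injections received and as the AERI denominator. If a per-occasion rate is also wanted, keep it as a separate line labelled per administration.
3. Reconcile the compliance ranges in SAP 11.1 and Table 9. State how a missing loading syringe and an unplanned extra syringe enter the compliance calculation.

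Items 1 and 2 cost some SAP wording and one derived variable. The eCRF already records whether one or two syringes were given, and two kit numbers for the loading dose, so no new data are needed. A compliance figure by syringe would need one check first: SAP 10.6 does not show whether the full-volume answer is captured for each loading syringe or once for the dose. All of this can be settled before database lock.
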